### 1471 **7.9.2. Criteria for Suspending/Stopping Overall Study**

1472 In the case of a system malfunction resulting in a severe hypoglycemia or severe hyperglycemia event  
1473 (as defined in Section 7.1) during closed-loop control either due to excess insulin administration or  
1474 inappropriate suspension that occurs more than one time, enrollment visits, randomization visits, and  
1475 all use of the closed-loop system in the study will be suspended while the problem is diagnosed. In  
1476 addition, study activities could be similarly suspended if the manufacturer of any constituent study  
1477 device requires stoppage of device use for safety reasons (e.g. product recall). The affected study  
1478 activities may resume if the underlying problem can be corrected by a protocol or system modification  
1479 that will not invalidate the results obtained prior to suspension.

1481 As stated in Section 7.6, the study DSMB will be informed of all serious adverse events and any  
1482 unanticipated adverse device events that occur during the study and will review compiled safety data at  
1483 periodic intervals. The DSMB will request suspension of study activities or stoppage of the study if  
1484 deemed necessary based on the totality of safety data available.

## CHAPTER 8: MISCELLANEOUS CONSIDERATIONS

## 8.1. Benefits

One purpose of this research is to reduce the frequency of hypoglycemia and severe hypoglycemic events. Hypoglycemia is the number one fear of many individuals and families with someone who has type 1 diabetes and this fear often prevents optimal glycemic control.

It is expected that this protocol will yield increased knowledge about using an automated closed-loop to control the glucose level. This research is a definitive step on the path towards development of a fully closed-loop system. In addition, it is the belief of the investigators that this study also presents prospect of direct benefit to the subjects and general benefit to others with diabetes.

## 8.2. Subject Compensation

Subjects will be compensated \$50 (or local equivalent) for each separate clinic visit during the study.

### 8.3. Subject Withdrawal

6.5. Subject Withdrawal  
Participation in the study is voluntary, and a subject may withdraw at any time. For subjects who withdraw, their data will be used up until the time of withdrawal.

## 8.4 Confidentiality

3.4. Confidentiality  
For security and confidentiality purposes, subjects will be assigned an identifier that will be used instead of their name. Protected health information gathered for this study will be shared with the coordinating center, the Jaeb Center for Health Research in Tampa, FL. De-identified subject information may also be provided to research sites involved in the study.

## CHAPTER 9: STATISTICAL CONSIDERATIONS

1511  
1512  
1513 The approaches to sample size and statistical analyses are summarized below. A detailed statistical  
1514 analysis plan will be written and finalized prior to the completion of the study.  
1515  
1516 The co-primary outcomes for this study are CGM-measured % below 70 mg/dL and % above 180  
1517 mg/dL over a 3-month period. The intervention will be considered effective if both of the following  
1518 comparisons between two treatment arms (SAP vs. CTR) are statistically significant ( $p < 0.05$ ):  
1519

- superiority test for % time CGM values below 70 mg/dL and
- non-inferiority test for % time CGM values above 180 mg/dL (non-inferiority limit = 5%).

  
1520  
1521  
1522 **9.1. Sample Size**  
1523 Sample size has been computed using co-primary outcomes of time  $<70$  mg/dL (superiority) and time  
1524  $>180$  mg/dL (non-inferiority). Data from the CGM arm of the JDRF CGM RCT from subjects meeting  
1525 the eligibility criteria for the current trial were used to project the distribution of % below 70 and above  
1526 180 mg/dL over 3 months as measured by CGM for the SAP group in the proposed study.  
1527  
1528 The total sample size was computed to be 110 for the following assumptions: (1) 1:1 randomization,  
1529 (2) 90% power, with adjustment to account for the two co-primary analyses, (3) a 50% relative  
1530 reduction in time  $<70$  mg/dL (or absolute reduction of 2.0% assuming baseline of 4.0%) with an  
1531 effective SD of 2.8% and 2-sided type 1 error of 5%, and (4) a non-inferiority limit of 5% for the  
1532 treatment group comparison of time  $>180$  mg/dL and assuming there is a true difference of 2.5%  
1533 favoring the CTR group, with an effective standard deviation of 11% and a 1-sided type 1 error of  
1534 2.5%. The sample size was increased to 126 to account for subjects with insufficient data to include in  
1535 the primary analysis (see section 9.2).  
1536  
1537 The Appendix provides further details of the sample size assumptions and computations.  
1538  
1539 **9.2. Calculation of Outcome Metrics and Handling of Missing Data**  
1540 *CGM Metrics*  
1541 Randomization is preceded by two weeks of blinded CGM run-in or by presenting at least three weeks  
1542 of personal CGM data. The two weeks of blinded run-in or the last two weeks of personal CGM data  
1543 will be used in the calculation of baseline CGM metrics.  
1544  
1545 Per protocol design, the first two weeks following the randomization visit involve a training schedule  
1546 for both groups. CGM data during this time will not be included in the calculation of the outcome  
1547 CGM metrics. Unblinded CGM data starting from Week 3 post-randomization through the 3 month  
1548 visit will be included in the calculation of each CGM metric. Missing (or less than 168 hours) post-  
1549 randomization unblinded sensor data will be imputed using all available post-randomization blinded  
1550 data. Subjects with any amount of post-randomization unblinded or blinded data will be included in  
1551 CGM analyses. Percentages  $<70$  and  $>180$  mg/dL will be calculated giving equal weight to each CGM  
1552 point for each subject.  
1553  
1554 The two weeks of blinded CGM data collected after 9 weeks will not be used for the primary outcome;  
1555 except for imputations as mentioned above.  
1556  
1557 *HbA1c*

1558 If the 3-month visit is completed but an HbA1c measurement from the central laboratory is not  
1559 available, a local HbA1c measurement made at the clinical site at the 3-month visit will be used if  
1560 available. In such cases the HbA1c value used in the analysis will be computed from a regression line  
1561 using the available lab-local HbA1c pairs. A similar imputation will be done for any missing lab  
1562 HbA1c values at baseline or other visits. If neither measurement at 3 months is available, then the  
1563 HbA1c value will be considered missing and the subject will be excluded from all HbA1c analyses.  
1564

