## CHAPTER 3: CGM RUN-IN PHASE

### 530 3.1. CGM Run-in Phase Overview

531 Concurrent with the screening and enrollment visit, the subject will be assessed for the need for  
532 CGM run-in activities prior to randomization.

533

534 Subjects who used a personal CGM that is the same brand as the study CGM prior to the study  
535 for at least 21 of the prior 28 days will proceed directly to randomization. These subjects will  
536 have the personal CGM downloaded for capture of two-week baseline data.

537

538 All other subjects will participate in the following CGM run-in phases requiring additional clinic  
539 visits as shown in Figure 7:

- 540 • Two-week period of blinded study CGM use to characterize baseline glycemic control;  
541 subjects using a personal CGM prior to the study will continue to use it during this  
542 period.
- 543 • Two-week period of unblinded study CGM use, with training in using CGM if necessary;  
544 subjects using a personal CGM prior to the study will discontinue the personal CGM  
545 beginning in this period.

546

547 Subjects participating in the CGM run-in phase will receive appropriate training on incorporating  
548 CGM into their diabetes management. Training will include the hypoglycemia and  
549 hyperglycemia safety protocols in section 6.1 as well as instruction that study CGM readings are  
550 affected by acetaminophen use and may be inaccurate for at least 4 hours if a medication  
551 containing acetaminophen is taken.

552

553 Subjects will receive supplies for blood glucose and ketone testing during this period:

- 554 • Blood glucose testing
  - 555 ○ Subjects will be provided with a study blood glucose meter, test strips, and  
556 standard control solution to perform quality control (QC) testing at home per  
557 manufacturer guidelines.
  - 558 ○ All study blood glucose meters will be QC tested with at least two different  
559 concentrations of control solution if available during all office visits. A tested  
560 meter will not be used in a study if it does not read within the target range at each  
561 concentration per manufacturer labeling. The subject will be instructed to contact  
562 study staff for a replacement of the meter, test strips, and control solution if a  
563 meter fails QC testing at home.
  - 564 ○ Subjects will be reminded to use the study blood glucose meter for all fingerstick  
565 blood glucose measurements during the run-in period.

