### 583 **3.2. Optimization of Insulin Pump Settings**

584 Data-driven optimization of pump settings will occur at the following times:

- 585 • Prior to Randomization:
  - 586 ○ At the Enrollment Visit for study subjects that do not need to complete a CGM run-  
587 in
  - 588 ○ At the Blinded CGM Run-in Review and Unblinded CGM Run-in Review Visits  
589 for study subjects participating in the CGM Run-in
- 590 • Following Randomization:
  - 591 ○ At the Week 2 visit for all study subjects (both the CTR and SAP Group).
  - 592 ○ If the study subject contacts the study physician due to concerns about their pump  
593 settings due to recurring hypo- or hyperglycemia.

594 Adjustments to pump settings (basal rates, correction factor, insulin-to-carbohydrate ratio, etc.)  
595 will be made in response to major trends observed in the CGM data, with flexibility for clinicians  
596 to adhere to guidelines and practices established at each individual practice rather than a fixed set  
597 of heuristics for all sites.

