### 600 **3.3. Blinded CGM Use**

601 At the screening visit, a CGM sensor will be placed for subjects who will complete the blinded  
602 CGM phase. The CGM receiver will be blinded so that the subject is not able to see the CGM  
603 glucose values. The subject will be instructed on sensor use including insertion of a new sensor  
604 after 7 days (or sooner if the sensor comes out) and will be asked to wear the sensor for 14 days.  
605 Additional sensors will be provided. Subjects that currently use a CGM may continue to use the  
606 personal CGM in addition to the blinded study CGM.

607 Subjects will be informed that in order to be eligible for the randomized trial, the blinded CGM  
608 must be used on a minimum of 11 out of 14 days.

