## CHAPTER 4: Randomized Trial

662  
663 **4.1. Randomization Visit**  
664  
665 **4.1.1. Timing of Visit**  
666 The randomization visit may occur concurrently with the Enrollment Visit for subjects who meet CGM  
667 use requirements described above. Otherwise, the visit will be concurrent with the Unblinded CGM  
668 Run-in Review Visit.  
669  
670 Subjects will receive supplies for blood glucose and ketone testing and associated use guidelines and a  
671 prescription for a glucagon emergency kit if needed, as described above. Subjects will be advised to  
672 contact the manufacturer's technical support center for technical issues with the study CGM and to call  
673 the study physician for any health related issues.  
674  
675 A urine pregnancy test will be repeated for all females of child-bearing potential who participated in  
676 the CGM run-in phase.  
677  
678 **4.1.2. HbA1c**  
679 HbA1c will be measured using DCA Vantage or similar POC device or local lab. A blood sample will  
680 also be drawn to send to the central laboratory for baseline HbA1c determination to be used in outcome  
681 analyses.  
682  
683 **4.1.3. Baseline C-Peptide Assessment**  
684 A blood sample will be drawn to send to the central laboratory for a random, non-fasting C-peptide  
685 determination to characterize baseline residual insulin production.  
686  
687 **4.1.4. Randomization**  
688 Eligible subjects will be randomly assigned to one of two treatment groups in a 1:1 ratio:  
689 1. Control-to-Range (CTR) Closed-Loop Group  
690 2. SAP Group  
691  
692 The subject's randomization group assignment is determined by completing a Randomization Visit case  
693 report form on the study website. The randomization list will use a permuted block design, stratified by  
694 clinical center.  
695  
696 *The subject will be included in the data analysis regardless of whether or not the protocol for the  
697 assigned randomization group is followed. Thus, the investigator must not randomize a subject until  
698 he/she is convinced that the subject/parent will accept assignment to either of the two groups.*  
699  
700 **4.1.5. Questionnaires**  
701 Subjects will complete a set of baseline questionnaires, described in section 5.1, prior to  
702 randomization. Subjects randomized into the CTR group will also complete an additional Technology  
703 Expectation Survey after randomization.  
704  
705 **4.2. Procedures for the CTR Group**  
706  

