#### 1573 **9.3.1. Changes in CGM-Measured % below 70 mg/dL from Run-in to 3-Months Post- 1574 Randomization Period between the Two Treatment Arms**

1575 Summary statistics (median, quartiles) will be reported for the CGM % <70 mg/dL by treatment group.

1576 Changes from run-in pre-randomization CGM wear (data generated as described above) to the 3-month  
1577 post-randomization period in CGM-measured % <70 mg/dL between two treatment arms will be  
1578 compared using a linear mixed effects regression model with a  $\log(x+0.005)$  transformation while  
1579 adjusting for the baseline CGM % <70 mg/dL and clinical center (random effect). Residual values will  
1580 be examined for an approximate normal distribution. If values are highly skewed even after the  
1581 transformation, then an alternate transformation or robust statistical method (e.g., non-parametric or  
1582 MM estimation) will be used instead.

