#### 1583 **9.3.2. Changes in CGM-Measured % above 180 mg/dL from Run-in to 3-Months Post- 1584 Randomization Period between the Two Treatment Arms**

1585 Summary statistics (median, quartiles) will be reported for the CGM % >180 mg/dL by treatment  
1586 group.

1587 Changes from run-in pre-randomization to over 3-months post-randomization in CGM-measured %  
1588 >180 mg/dL between two treatment arms will be compared using a linear mixed effects regression  
1589 model; while adjusting for % >180 during run-in, and clinical center (random effect). A 2-sided 95%  
1590 confidence interval for the difference between treatment arms will be generated. Separate two-sided p-  
1591 values will be calculated to test non-inferiority and superiority. Since non-inferiority is often denoted  
1592 in terms of a one-sided test, it is worth noting that a two-sided test at alpha = 0.05 gives the same  
1593 rejection region in the right tail as a one-sided test at alpha = 0.025. It is also worth noting that the  
1594 additional hypothesis test for superiority does not inflate the overall alpha since a type 1 error can only  
1595 occur if the two-sided 95% confidence interval fails to contain the true difference. Residual values will  
1596 be examined for an approximate normal distribution. If values are highly skewed then a  
1597 transformation or robust statistical method (e.g., non-parametric or MM estimation) will be used  
1598 instead.

1599  
1600  
1601  
1602  
1603

1604 **9.4. Secondary Efficacy Analyses**  
1605 In secondary analyses, treatment group differences will be assessed for additional CGM metrics and  
1606 HbA1c. For all secondary analyses (including sections 9.5, 9.6, and 9.7), the false discovery rate will  
1607 be controlled using the adaptive Benjamini-Hochberg procedure with <0.10 as the threshold for  
1608 statistical significance.

1609  
1610 Secondary glycemic metrics based on CGM data will include the following outcomes:  
1611

1612 **CGM Metrics Related to Overall Control**  
1613 - mean glucose  
1614 - % in range of 70-180 mg/dL  
1615 - % in range 70-140 mg/dL  
1616 - glucose variability measured with the coefficient of variation  
1617

1618 **CGM Metrics Related to Hypoglycemia**  
1619 - % <60 mg/dL  
1620 - % <54 mg/dL  
1621 - low blood glucose index  
1622 - hypoglycemia events (defined as at least 15 consecutive minutes <70mg/dL)  
1623

1624 **CGM Metrics Related to Hyperglycemia**  
1625 - % >250 mg/dL  

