1626 - % >300 mg/dL  
1627 - high blood glucose index  
1628

1629 The analyses for the above CGM will parallel those mentioned above for the primary % below 70  
1630 mg/dL outcome, with the exception that a transformation will not be used for those metrics with a  
1631 distribution that is approximately normally distributed. Summary statistics will be reported mean  $\pm$  SD  
1632 or median (quartiles) as appropriate to the distribution.  
1633

1634 A comparison of primary and secondary results during the daytime and overnight will be made.  
1635

1636 **HbA1c**  
1637 Change in HbA1c from baseline to 13 weeks will be compared between the two treatment arms using a  
1638 linear model while adjusting for baseline HbA1c and clinical center (random factor).  
1639

1640 Several binary outcomes will be compared between treatment groups using central lab HbA1c values.  
1641 • HbA1c <7.0% at 13 weeks  
1642 • HbA1c <7.5% at 13 weeks  
1643 • HbA1c improvement from baseline to 13 weeks  $\geq$ 0.5%  
1644 • HbA1c improvement from baseline to 13 weeks  $\geq$ 1.0%  
1645 • HbA1c relative improvement from baseline to 13 weeks  $\geq$ 10%  
1646 • HbA1c improvement from baseline to 13 weeks  $\geq$ 1.0% or HbA1c <7.0% at 13 weeks  
1647

1648 Our goal is to minimize the amount of missing data and it is worth noting that all statistical methods  
1649 for handling missing data rely on untestable assumptions and there is no one correct way to handle  
1650 missing data. If some HbA1c data will be missing, in addition to the completer-only analyses

1651 mentioned above, sensitivity analyses will be performed in order to confirm that the conclusions do not  
1652 rely on the statistical methods employed for handling missing data. Replication of the HbA1c analyses  
1653 with imputed data for subjects with missing both local and central lab HbA1c at 13 weeks will be done  
1654 using two methods:

- Rubin's multiple imputation and
- Direct likelihood

1657

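### Do the co-primary models need an entry-pathway term because the baseline CGM value comes from two different sources?

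*Combined protocol and SAP*

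**What the plan says.** Section 3.1 defines two routes into the trial. "Subjects who used a personal CGM that is the same brand as the study CGM prior to the study", on at least 21 of the prior 28 days, go directly to randomization. Everyone else does two weeks of blinded and then two weeks of unblinded study CGM. In the blinded phase, "The CGM receiver will be blinded so that the subject is not able to see the CGM" values, although anyone who already has a personal CGM may keep using it alongside (3.1, 3.3). Section 3.2 gives run-in subjects two pump-setting reviews before randomization, "At the Blinded CGM Run-in Review and Unblinded CGM Run-in Review Visits", and gives direct entrants one, at enrollment.

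Section 9.2 then takes "The two weeks of blinded run-in or the last two weeks of personal CGM data" as the source of the baseline metrics. The % <70 model in 9.3.1 is described as "adjusting for the baseline CGM % <70 mg/dL and clinical center (random effect"), and the % >180 model in 9.3.2 has the same structure. Section 9.4 carries the approach to the secondary CGM metrics. On allocation, 4.1.4 says "The randomization list will use a permuted block design, stratified by" clinical center. Pathway is not a covariate, a stratum, a listed subgroup or a sensitivity analysis. Chapter 9 describes itself as a summary, with a detailed statistical analysis plan to follow before study completion.

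**The concern.** The same baseline reading may mean different things on the two routes. A direct entrant's baseline is recorded on a CGM that the subject can see and already relies on. A run-in subject's baseline is recorded on a masked study device, before two weeks of unblinded use and an additional settings review. The outcome is measured on unblinded CGM for nearly everyone. If run-in subjects end up with different outcomes at the same baseline value, a model with one intercept and one slope leaves that gap in the residual.

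The planning correlations of 0.74 and 0.80 in the Appendix come from a single-source baseline, so they do not show how well a mixed baseline predicts. At stake would be precision in both co-primary comparisons, which could be recovered by a covariate known for every subject before randomization.

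**Working it through.** **1. Validity.** Pathway is determined before randomization, so omitting it cannot bias the arm comparison. In simulated trials (N = 110, half via run-in, pathway gaps of 0, 1 and 2 points of % <70 at equal baseline), type 1 error without the term was 0.044 to 0.050.

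**2. The plan's power figures.** From 9.1 and the Appendix, N = 110, so SE = SD × √(4/110).
- % <70: 2.8 × 0.1907 = 0.534; Φ(2.0/0.534 − 1.96) = 96.3%.
- % >180: 11 × 0.1907 = 2.098; distance to margin 5 + 2.5 = 7.5; Φ(7.5/2.098 − 1.96) = 94.7%.
- The noncentral t gives 96.0% and 94.3%, and 96.0 + 94.3 − 100 = 90.3%.

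These agree with the stated 96%, 94% and at least 90%. They use a baseline–outcome correlation of 0.5 instead of the observed 0.74 and 0.80, which leaves room for a noisier mixed baseline.

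**3. What the term would do for % >180.** Inputs from the documents: N = 126, about 7 centers, SD 13. Assumed: half the subjects via run-in; within-pathway correlation ρ of 0.8 or 0.5; baseline difference d between pathways; fraction k of d that is still present in the outcome.

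At equal baseline the pathways then differ by g = (k − ρ)d. Omitting the term adds 0.25 × g² × 169/(169 + 0.25d²) to the within-pathway residual variance 169(1 − ρ²). Including it costs one degree of freedom, a factor of about 116/115 = 1.0087 (centers counted as fixed effects).

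Worked case, ρ = 0.8, d = 4, k = 0: g = −3.2; added variance 0.25 × 10.24 × 169/173 = 2.50; residual 60.84 + 2.50 = 63.34. Ratio (60.84/63.34) × 1.0087 = 0.969, or 3.1% better.

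Same case with k = 0.5: g = −1.2; added variance 0.25 × 1.44 × 169/173 = 0.35; ratio (60.84/61.19) × 1.0087 = 1.003, or 0.3% worse.

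Change in the variance of the treatment difference from adding the term:

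| ρ | k | d = 4 | d = 8 |
|---|---|---|---|
| 0.8 | 0 | 3.1% better | 12.6% better |
| 0.8 | 0.5 | 0.3% worse | 1.3% better |
| 0.8 | 0.75 | 0.9% worse | 0.8% worse |
| 0.5 | 0 | 0.1% worse | 2.0% better |
| 0.5 | 0.5 | 0.9% worse | 0.9% worse |

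The sign turns on how k compares with ρ. When the baseline difference persists to about the extent that the baseline slope predicts, the existing covariate already absorbs it. The documents do not give k, d or the pathway split.

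**4. Effect on the non-inferiority decision.** At N = 126 and SD 11, SE = 11 × √(4/126) = 1.96 and power is Φ(7.5/1.96 − 1.96) = 96.9%. A 1% rise in variance gives 96.8%; a 7% fall gives 97.8%.

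The 12.6% gain arises only at ρ = 0.8, where power is not in question. The residual SD without the term is √70.19 = 8.38, SE = 8.38 × 0.1782 = 1.493, and power is Φ(7.5/1.493 − 1.96) = 99.9%.

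**5. Effect on the superiority decision.** On the planned log(x + 0.005) scale, 4.0% against 2.0% is ln(0.045/0.025) = 0.588. Simulated standard errors at N = 126 and log-scale correlation 0.74 were 0.0687 to 0.0713, so z is 0.588/0.0713 = 8.2 to 0.588/0.0687 = 8.6. At a correlation of 0.5 the larger SE grows by √(0.75/(1 − 0.74²)) = 1.29 to 0.092, and z is still 6.4. Power exceeds 99.99% throughout.

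**The case for a change.** The best case for the term is asymmetry. It costs one degree of freedom, about 1% of variance (up to 1.4% in simulation), and needs no new data. If the pathways really do differ at equal baseline, the gain can be several times larger. On the untransformed scale of the sample size section, with N = 110 and half the subjects via run-in, simulated power for % <70 rose from 93.0% to 94.9% when that gap was 2 points. For % >180 it rose from 92.3% to 93.3% when the gap was 5 points.

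This stands as arithmetic, and a statistician who adds the term in the detailed analysis plan does no harm. But a 2-point gap in % <70 at equal baseline equals the whole assumed treatment effect. With a 1-point gap the change was 94.6% to 95.0%, and with none it was 95.2% to 95.1%. Nothing in the documents points to the larger gaps. The Appendix comparison of early and later periods (27% and 27% for % >180; 3.7% and 4.0% for % <70) draws both periods from the open-loop CGM arm of one trial, so it neither shows nor excludes a gap.

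The two-level term is also a blunt proxy for the proposed mechanism. The run-in group mixes subjects with no CGM and subjects who still watch a personal CGM during the blinded weeks.

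**Conclusion.** The concern does not hold. The plan does pool two baseline sources without a pathway term, but the comparison remains unbiased, type 1 error is controlled and the stated power reproduces. The claimed gain rests on a pathway split and a shift that the documents do not give, and its larger values also need a baseline difference that vanishes entirely by follow-up. Under other plausible assumptions the term does nothing or costs just under 1% of variance. At the planning SD of 11 and N = 126, non-inferiority power moves from 96.9% to 96.8% if variance rises 1% and to 97.8% if it falls 7%. Superiority power on the planned log scale is above 99.99% with or without the term. Whether to include it is a matter of preference on which reasonable statisticians would differ.
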